## 14.6. Data Computations and Data Imputations

### 14.6.1. Time to [REDACTED] Confirmed Perceptible [REDACTED] Pain Relief (TCPR)

[REDACTED] Time to confirmed perceptible pain relief is defined as the time (in minutes) to perceptible pain relief as indicated on the first stopwatch, provided that the subject also stopped the second stopwatch indicating meaningful pain relief. [REDACTED]

[REDACTED]  
[REDACTED] subjects who do not have relief by 12 hours, who take rescue medication before having relief, or who discontinue before having relief will have time to relief set to 12 hours and be censored at 12 hours

**14.6.2.** [REDACTED]

[REDACTED]

**14.7. Analysis Methods**

**14.7.1. [REDACTED] Time to Confirmed Perceptible Pain Relief**

[REDACTED] time to confirmed perceptible pain relief (TCPR), [REDACTED] will be analyzed using survival data analysis. The survival function (cumulative proportions of subjects with pain relief at each time point) and the median survival time will be estimated by the Kaplan-Meier method for each treatment. The survival functions will be compared using the Wilcoxon test.

Sensitivity analyses will be conducted for TCPR assessing the impact of censoring at the time of rescue medication for subjects not having meaningful relief, and also the impact of censoring at the time of perceptible relief for subjects not having meaningful relief. Further details regarding these analyses will be provided in the statistical analysis plan.

**14.7.2. Earliest Statistically Significant Separation of Test NPX and Placebo on Percentage of Subjects with Confirmed Perceptible Relief**

The earliest time of separation between Test NPX and placebo will be established by comparing the percentage of subjects with confirmed perceptible pain relief starting from 45 minutes to successively earlier minutes in one-minute increments, until statistical significance is no longer achieved. The dichotomized response will be analyzed using logistic regression analysis.

**14.7.3.**

[REDACTED]

[REDACTED]

**14.7.4.**

[REDACTED]

[REDACTED]

[Section 14.6.2.](#)

**14.7.5.**

[REDACTED]

[REDACTED]

**14.7.6.**

[REDACTED]

[REDACTED]

**14.7.7.**

[REDACTED]

[REDACTED]

[Section 14.6](#)

**14.7.8. Subgroup Analyses**

Time to confirmed perceptible relief will be analyzed based on the following subgroups: age group (<18 years, ≥18 years), gender, race (white, non-white) and baseline categorical pain

Test Naproxen Sodium 220 mg Tablet

Protocol: CCSPAA000457

Version 1: 11 May 2018

Version 2: 19 July 2018 - Administrative Change/Non-substantial Amendment 1

(moderate, severe). The survival function and the median survival time will be estimated by the Kaplan-Meier method within each subgroup.

## **14.8. Safety Analysis**

The safety analysis will be based on the safety analysis set.

### **14.8.1. Adverse Events**

Treatment-emergent AEs are those with a start date and time at or after the time of study drug administration. All summaries described below are for treatment-emergent AEs except where noted. Non- treatment-emergent AEs will be provided in a listing.

The number and percentage of subjects experiencing AEs will be tabulated by treatment, system organ class and preferred term using the MedDRA coding dictionary. The number and percentage of subjects experiencing treatment-related AEs will also be presented by system organ class and preferred term. Treatment-related AEs will include events marked as being at least possibly related to study treatment. The number and percentage of subjects with AEs will be presented by severity. Subjects will be counted only once for each system organ class and preferred term by selecting the most severe event. The number of subjects with the most commonly reported adverse events (those reported by 5% or more in any one treatment group) will be summarized by treatment, system organ class and preferred term. The number of subjects with adverse events will also be summarized by demographic characteristics: age group (<18 years, ≥18 years), gender, and race.

The number and percentage of subjects experiencing SAEs or who discontinued the study due to an AE will be presented by system organ class and preferred term. These displays will include all AEs, not just treatment-emergent AEs.

## **15. DIRECT ACCESS TO SOURCE DATA/DOCUMENTS**

The investigator (s)/institutions(s) will permit study related monitoring, audits, IRB/IEC review, and regulatory inspection(s) by providing access to the source data/documents.

### **15.1. Study Monitoring**

Before an investigational site can enter a subject into the study, a representative of JJCI will visit the investigational study site to:

- Determine the adequacy of the facilities
- Discuss with the investigator(s) and other personnel their responsibilities the site's responsibility with regard to protocol adherence as well as the study and monitoring responsibilities of J&J or its representatives. These responsibilities will be documented in a Clinical Study Agreement between J&J and the investigator.

During the study, a monitor from J&J or representative will have regular contacts with the investigational site, for the following:

- Provide information and support to the investigator(s)
- Confirm that facilities remain acceptable
- Confirm that the investigational team is adhering to the protocol, that data are being accurately recorded in the CRFs, and that investigational product accountability checks are being performed
- Perform source data verification. This includes a comparison of the data in the CRFs with the subject's source documents, e.g., written medical records, electronic medical records at the hospital or practice, subject diaries/journals and other records relevant to the study. This will require direct access to all original records for each subject (e.g., clinic charts).
- Record and report all protocol deviations not previously sent to J&J. The Investigator should not deviate from the Protocol except if specified by the Sponsor or within the Protocol.
- Confirm AEs and SAEs have been properly documented on CRFs and confirm any SAEs have been forwarded to J&J and those SAEs that met criteria for reporting to Regulatory Authority/Competent Authority and/or IRB/IEC, as applicable, have been forwarded to the required authorities. The monitor will be available between visits if the investigator(s) or other staff needs information or study-related direction.

**COMPANY CONFIDENTIAL**

Test Naproxen Sodium 220 mg Tablet

Protocol: CCSPAA000457

Version 1: 11 May 2018

Version 2: 19 July 2018 - Administrative Change/Non-substantial Amendment 1

## **15.2. Audits and Inspections**

Authorized representatives of J&J, a regulatory/competent authority, an IRB/IEC representative may visit the site to perform audits or inspections, including source data verification. The purpose of a J&J audit or inspection is to systematically and independently examine all study-related activities and documents to determine whether these activities were conducted, and data were recorded, analyzed, and accurately reported according to the protocol, GCP guidelines of the ICH E6, and any applicable regulatory requirements. The investigator should notify the Sponsor (e.g., Study Manager, Monitor) listed within the protocol or other contacts provided immediately if contacted by a regulatory agency about an inspection.

**COMPANY CONFIDENTIAL**

## **16. QUALITY CONTROL AND QUALITY ASSURANCE**

The clinical study will be executed and reported following GCPs, all applicable regulatory requirements and applicable SOPs, including quality control of documents. Deviations will be analyzed and documented. To ensure compliance, the Sponsor may conduct one or several quality assurance audit(s). Please see [Section 15.2](#) for more details regarding the audit process.

## **17. DATA HANDLING AND RECORDKEEPING**

### **17.1. Case Report Forms / Electronic Data Capture**

All data will be collected on source documents first and then recorded in an Electronic Data Capture (EDC) system. The EDC system is the database where pertinent study data are collected such as demography, subject randomization, efficacy assessments, adverse events, and subject disposition. EDC CRFs should be completed for each included subject. The completed pages of the EDC system are the sole property of the Sponsor and should not be made available in any form to third parties, except for authorized representatives of the Sponsor or appropriate regulatory authorities, without written permission from the Sponsor.

It is the Investigator's responsibility to ensure completion and to review and approve all information captured in the EDC. The subject's data in the EDC system must be electronically signed by the Investigator. These signatures serve to attest that the information contained in the EDC system is true. At all times, the Investigator has final personal responsibility for the accuracy and authenticity of all clinical and laboratory data entered in the EDC. Subject source documents are the Investigator's/physician's subject records maintained at the study site. In cases where the source documents are the hospital or the physician's chart, the information collected in the EDC must match those charts. All final data recorded in EDC system will be copied into files and kept by the Sponsor. A copy of these files will also be kept at the clinical site. All data provided in the CRF must be supported by source document.

### **17.2. Source Documents**

The investigator/institution should maintain adequate and accurate source documents and trial records that include all pertinent observations on each of the site's trial subjects. Source data should be attributable, legible, contemporaneous, original, accurate, and complete. Changes to source data should be traceable, should not obscure the original entry, and should be explained if necessary (e.g., via an audit trail). Inspection and Retention of Records

### **17.3. Inspection and Retention of Records**

To enable evaluations and/or audits from regulatory authorities or the Sponsor, the investigator agrees to keep records including the identity of all participating subjects (sufficient information to link records, e.g., CRFs and hospital records), all original signed informed consent forms, copies of all CRFs, SAE forms, source documents, and detailed records of treatment disposition.

The PI must maintain all documentation relating to the study according to ICH guidelines or as specified in the Clinical Study Agreement for a period of 2 years after the last marketing application approval or per local requirements if longer than 2 years, or if not approved 2

Test Naproxen Sodium 220 mg Tablet

Protocol: CCSPAA000457

Version 1: 11 May 2018

Version 2: 19 July 2018 - Administrative Change/Non-substantial Amendment 1

years following the discontinuance of the test article for investigation. If it becomes necessary for J&J or the Regulatory Authority to review any documentation relating to the study, the Investigator must permit access to such records.

If the investigator relocates, retires, or for any reason withdraws from the study, the Sponsor should be prospectively notified. The study records must be transferred to an acceptable designee, e.g., another investigator. The investigator must obtain Sponsor's written permission before disposing of any records, even if retention requirements have been met.

## **18. PUBLICATION POLICY**

Publication of study results by the Investigator is discussed in the Clinical Study Agreement, as appropriate. Results from this study may be published in the form of oral or written presentations at scientific meetings or as one or more peer-reviewed journal articles. In these cases, no information on individual subjects will be revealed.

## **20. APPENDICES**

**COMPANY CONFIDENTIAL**

Test Naproxen Sodium 220 mg Tablet  
Protocol: CCSPAA000457  
Version 1: 11 May 2018  
Version 2: 19 July 2018 - Administrative Change/Non-substantial Amendment 1

**APPENDIX 1:**

**PAIN RATING SCALES/ CATEGORICAL PAIN INTENSITY SCALE**

Finish the statement “My pain at this time is” by checking the appropriate box.

No Pain (0)

Mild Pain (1) Moderate Pain (2) Severe Pain (3)

**0-10 PAIN INTENSITY - NUMERICAL RATING SCALE (PI-NRS)**

Circle the number that best represents your pain.

No pain 0 1 2 3 4 5 6 7 8 9 10 Very severe pain

[Redacted response area]

Test Naproxen Sodium 220 mg Tablet  
Protocol: CCSPAA000457  
Version 1: 11 May 2018  
Version 2: 19 July 2018 - Administrative Change/Non-substantial Amendment 1

**APPENDIX 2:** [REDACTED]

[REDACTED]

[REDACTED]

[REDACTED]

[REDACTED]

[REDACTED]

[REDACTED]

## 1 INTRODUCTION

Naproxen is a propionic acid derivative and nonsteroidal anti-inflammatory drug (NSAID) with analgesic and antipyretic properties. The mechanism of action of naproxen involves inhibition of cyclooxygenase enzymes resulting in decreased prostaglandin synthesis. The sodium salt of naproxen has been developed as a more rapidly absorbed formulation of naproxen. Naproxen sodium products have been available over-the-counter (OTC) for the indications of fever reduction and relief of minor aches and pains in several countries for many years. According to the Drug Facts for [REDACTED], dosing for adults and children 12 years of age and older is one 220 mg dosage unit (e.g., tablet, caplet, capsule) every 8-12 hours, and for the first dose, may take two 220 mg units within the first hour. [REDACTED]

Clinical efficacy and safety studies have not yet been conducted on the [REDACTED] formulation of naproxen sodium. The current study will evaluate the analgesic onset, efficacy and safety of a single 440 mg dose of [REDACTED] naproxen sodium (administered as two 220 mg tablets) compared to two currently marketed [REDACTED] formulations of naproxen sodium and placebo after third molar dental extractions. The postoperative dental pain model is a validated model of acute pain that is widely used to study analgesic efficacy of compounds.

### 1.1 Study Objectives

To evaluate analgesic onset, efficacy, and safety of a single dose of 440 mg of naproxen sodium administered as two Test Naproxen Sodium 220 mg tablets (Test NPX) compared with two commercial naproxen sodium products (two [REDACTED] 220 mg tablets and two [REDACTED] 220 mg [REDACTED] capsules) and placebo in the dental pain model following third-molar extractions.

### 1.2 Study Design

This is a single-dose, randomized, double-blind, placebo- and active- controlled, parallel-group study to evaluate the analgesic onset, efficacy, and safety profile of 440 mg of naproxen sodium administered as two Test NPX 220 mg tablets compared with two commercial products and placebo over a 12-hour period after third-molar extractions. Subjects will undergo dental extraction of three or four third molars. Maxillary third molars may be removed regardless of impaction level. The mandibular extractions must meet one of the following scenarios and must not result in a trauma rating of severe in a mild, moderate, or severe scale:

- two full bony impactions
- two partial bony impactions

- one full bony impaction in combination with one partial bony impaction

Pain assessments will be based on subject self-report. Subjects who meet the randomization criteria (post-surgical pain of moderate to severe on the four-point categorical pain scale [0-no pain, 1-mild pain, 2-moderate pain, 3-severe pain], and at least a score of 5 on the 11-point [0-10] pain intensity numerical rating scale [PI-NRS] at baseline within 4.5 hours of last stitch from dental extractions) will be assigned to one of four treatment groups. This PI-NRS will be within 5 minutes prior to study medication dosing and will be considered the time 0 pain intensity assessment.

Approximately 500 subjects will receive a single 440 mg dose of either Test NPX, [REDACTED] tablets, [REDACTED] capsules, or placebo in a 3:3:3:1 allocation ratio and will be stratified according to gender and baseline pain rating (moderate or severe). To maintain the double-blind nature of the study, an independent third party will administer study drug to blindfolded subjects. No less than approximately 30% of randomized subjects will be either male or female. In addition, no more than approximately 30% of subjects will be 17 years of age at the time of screening.

Self-reported pain intensity will be collected at baseline (time 0). [REDACTED]

[REDACTED] Perceptible pain relief and meaningful pain relief will be collected using two separate stopwatches. Subjects who do not experience any pain relief after dosing will be encouraged, but not required, to wait at least 1.5 hour before using rescue therapy. [REDACTED]

After completion of all study assessments, subjects will be discharged from the study site. Subjects will be interviewed by telephone to follow up on appropriate postsurgical medical care and changes in their health, including any emergent or existing AEs. The interview will occur between Day 6 – 10 of the study.

**Table 1: Schedule of Activities**

	Screening	Baseline (Day of Surgery)	Hours Post-Dose	Follow-Up Call/End of Study
Procedures	Day -30 to 1	Day 1	0 to 12 hours	Day 6 - 10
Written informed consent and/or assent	X			
Demography (including age)	X			
Inclusion / Exclusion Assessment	X	X		
Significant medical history	X	X		
Vital signs	X	X		
Physical Exam (Height, weight and BMI)	X			
Urine pregnancy test (Females of childbearing potential)	X	X		
Urine drug screen	X	X		
Serology	X			
Dental extraction surgery		X		
Baseline Pain Assessments (Categorical and PI-NRS)		X 		
Randomization criteria		X		
Investigational product administration		X		
Stopwatch Assessments (perceptible & meaningful pain relief)			X	
[REDACTED]			X	
Rescue therapy			X 	
[REDACTED]			X 	
Prior and Concomitant Therapy	X	X	X	X 
Safety monitoring 	X	X	X	X
Subject Disposition				X 

 Scored within 4.5 hours after last stitch from dental surgery; [REDACTED]  
 [REDACTED]  
 [REDACTED];  Subjects encouraged to wait at least 1.5 hours after investigational product administration before using rescue medicine; [REDACTED]  
 [REDACTED]  Medications and other treatments taken after 12-hour assessment period through follow-up interview will be captured on source documents and only those taken for or associated with an AE will be recorded in the CRF;  Collection of AEs and report of pregnancy;  End of Study for each subject is defined as the follow-up phone call or early termination.

## 2 INTERIM ANALYSES

No interim statistical analysis is planned for this trial.

## 3 ANALYSIS SETS

### 3.1 Primary Analysis Set

The primary analysis set for the efficacy analyses will be all randomized subjects.

Subjects who received different treatment from their assigned treatment according to the sponsor-intended treatment decodes will be analyzed based on the actual received treatment.

### 3.2 Per-Protocol Set

As a secondary analysis, the primary endpoint will be analyzed based on the per-protocol analysis set, if the per-protocol analysis set differs from the primary analysis set by at least 5% of the subjects.

The per-protocol set will exclude subjects who took rescue medication within 90 minutes after dosing, vomited within 60 minutes after dosing, and those with major protocol deviations having potential substantial impact on the efficacy evaluation. The per-protocol set will be determined before unblinding.

### 3.3 Safety Analysis Set

The Safety Analysis Set will include all subjects who are randomized and take investigational product. Safety analysis will be based on the actual received treatment.

## 4 EFFICACY ASSESSMENTS AND ENDPOINTS

### 4.1 Efficacy Assessments

- Time to perceptible pain relief (TPPR)– recorded using perceptible pain relief stopwatch
- [REDACTED]
- Time to confirmed perceptible pain relief (TCPR) – defined as the time to perceptible pain relief provided that the subject subsequently stopped the meaningful pain relief stopwatch
- Pain intensity

Categorical 4-point scale: 0 – no pain, 1 – mild pain, 2 – moderate pain and 3 – severe pain, collected at baseline.

Numerical 0 – 10 scale (PI): 0 – no pain to 10 – very severe pain, collected at Baseline

- [REDACTED]

- [REDACTED]

- [REDACTED]

## 4.2 Efficacy Endpoints

### Primary efficacy endpoint

- Time to confirmed perceptible pain relief (TCPR)

### Secondary efficacy endpoints

- Percentage of subjects with confirmed perceptible pain relief from 45 minutes to successively earlier minutes in one-minute increments (Test NPX versus PBO)

### Tertiary efficacy endpoints

- [REDACTED]

- [REDACTED]

- [REDACTED]

- [REDACTED]

- [REDACTED]

- [REDACTED]

- [REDACTED]

- [REDACTED]

- [REDACTED]

- [REDACTED]

### 4.3 Safety Assessments and Endpoints

- Number and percentage of subjects with treatment-emergent adverse event (AE)
- Number and percentage of subjects who discontinued the study due to an AE
- Number and percentage of subjects experiencing a serious AE
- Number and percentage of subjects with treatment-related AEs
- Number and percentage of subjects with treatment-emergent AE by severity and relationship to treatment

### 4.4 Covariates

No covariate variable will be adjusted in the analyses.

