**COMPANY CONFIDENTIAL**

## **10.5. Randomization/Treatment Allocation**

The randomization schedule will be generated by the Sponsor to ensure treatment blinding. The site will keep the randomization schedule in a locked, secured area with access limited to only the assigned third-party person(nel), back-up staff member, and un-blinded monitor. After meeting the appropriate post-surgery criteria, subjects will be randomized to receive one of four treatments (Test NPX 440 mg, [REDACTED] tablet 440 mg, [REDACTED] 440 mg or placebo) in a 3:3:3:1 ratio. Subjects will be stratified by gender and baseline pain (moderate or severe). For subjects with moderate baseline pain, randomization numbers will be assigned to subjects in sequential order starting with the lowest available number within the appropriate gender stratum. Similarly, for subjects with severe baseline pain intensity, subjects will be assigned in sequential order starting with the highest available number in the appropriate gender stratum.

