### **14.1. Sample Size Determination**

A sample size of 150 per group for the active treatment arms was chosen based on pharmacokinetic/pharmacodynamics modeling and simulation using data from previous studies[3]. Based on the modeling, it was determined that 150 subjects per active treatment arm would be needed to provide 90% power to reject the null hypothesis of equal distributions for time to confirmed perceptible relief, when comparing Test NPX tablets with [REDACTED] tablets, using a two-sided test at the 0.05 significance level. A sample size of at least 50 subjects per treatment arm provides greater than 90% power to reject the null hypothesis of equal distributions for time to confirmed perceptible relief when comparing Test NPX tablet and placebo assuming median times to relief of 17 minutes for Test NPX and at least 2 hours for placebo.

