### 5.3.2 Earliest Statistically Significant Separation of Test NPX and Placebo on Percentage of Subjects with Confirmed Perceptible Relief

The earliest time of separation between Test ██████ and PBO will be established by comparing the percentage of subjects with confirmed perceptible pain relief starting from 45 minutes to successive earlier minutes in one-minute increments, until statistical significance is no longer achieved. At each one-minute increment, each subject will be categorized as either having experienced confirmed perceptible pain relief by that time or not. The resulting binary response at each time point will be analyzed using logistic regression analysis.

The following is sample SAS code for the logistic regression analyses:

```
proc GENMOD data=DATASET ;  
  
  class trt;
```

```
model responder = trt / dist=BIN link=LOGIT;  
lsmeans trt / diff cl exp;  
run;
```

5.3.3

[REDACTED]

[REDACTED]

[REDACTED]

5.3.5

[REDACTED]

[REDACTED]

[REDACTED]

5.3.6 [REDACTED]

5.3.7 [REDACTED]

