**5.3.8 Subgroup Analyses**

Time to confirmed perceptible relief will be analyzed based on the following subgroups: age group (<18 years, ≥18 years), gender, race (white, non-white) and baseline categorical pain (moderate, severe). The survival function and the median survival time will be estimated by the Kaplan-Meier method within each subgroup.

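### Randomisation is stratified by gender and baseline pain but the SAP bars adjustment: the planned tests are valid, but the active-comparator tests lose power if the strata predict time to relief.

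*SAP*

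**What the plan says.** Protocol 10.5: "Subjects will be stratified by gender and baseline pain (moderate or severe"), with allocation "in a 3:3:3:1 ratio" across the four arms. SAP 1.2 allows unequal strata: "No less than approximately 30% of randomized subjects will be either male or female".

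SAP 4.4 is one sentence: "No covariate variable will be adjusted in the analyses". The code agrees. In SAP 5.3.1 treatment is the only variable on the LIFETEST strata statement, and the onset model in SAP 5.3.2 is "model responder = trt / dist=BIN link=LOGIT". In the visible text gender and baseline pain return only in SAP 5.3.8 ("Time to confirmed perceptible relief will be analyzed based on the following subgroups"), as Kaplan-Meier estimates within each subgroup. The two TCPR sensitivity analyses in SAP 5.3.1 change the censoring rule only.

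Protocol 14.1 sizes the active arms on Test NPX against the marketed tablet: "150 subjects per active treatment arm would be needed to provide 90% power". SAP Table 2 gives each TCPR test alpha 0.049. The onset endpoint is tested at 0.05 only if all three TCPR tests succeed, and otherwise at 0.001.

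**The concern.** Stratified allocation balances the arms on gender and pain. If those factors affect time to relief, the between-stratum part of the outcome variation can no longer contribute to the difference between arms. The unstratified Wilcoxon variance still includes it. The standard error is then too large, the rejection rate under the null falls below nominal, and power falls with it. If the factors do not affect time to relief, nothing is lost.

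The active-comparator tests are where this could matter. They are planned at 90% power, so they have little reserve. Both must succeed to release 0.05 for the onset endpoint, so a loss on each compounds. No reason for leaving the strata out is given.

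**Working it through.** **1. The plan's own figures.** The active-comparison 90% cannot be reproduced, because its effect size comes from modelling on file. Inverting Schoenfeld's formula, HR = exp{2(z₀.₉₇₅ + z₀.₉₀)/√d} with z-sum 3.2415, gives 1.45 for d = 300 events and 1.56 for d = 210. Testing at 0.049 instead of 0.05 changes 90% to Φ(3.2415 − 1.9686) = 89.8%.

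The placebo figure does reproduce. Exponential medians of 17 and 120 minutes give HR 120/17 = 7.06. The events needed for 90% power are 4 × 3.2415²/(ln 7.06)² = 11.0, so 12, against about 99 expected with 50 per arm. Simulated Wilcoxon power is 1.00.

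**2. Inputs to the comparison.**
- From the documents: 150 per active arm, alpha 0.049, Test NPX median 17 minutes (used in the reference stratum), all non-events ranked last and tied at 12 hours.
- Assumed: exponential times; 10% never relieved; allocation balanced within strata; treatment HR 1.72, chosen to give about 90% Wilcoxon power when the strata are inert. This is larger than the Schoenfeld values because the Wilcoxon test is less efficient than the log-rank test under proportional hazards and because of the ties at 12 hours.
- Assumed splits: A, 45% severe and 50% male; B, 30% and 40%; C, 25% and 30%.
- Assumed prognostic strength: the HR pairs in the table (pain, moderate v severe / gender).

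**3. The stratified statistic.** Z = Σ wU / √(Σ w²V). U is the within-stratum rank sum minus its expectation, V its tie-corrected variance, and w = 1/(stratum size + 1), counting the two arms compared.

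**4. Power, unstratified → stratified (%).** 30,000 trials per scenario; standard error of the paired difference at most 0.15 point.

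| Pain HR / gender HR | Split A | Split B | Split C |
|---|---|---|---|
| 1 / 1 | 89.8 → 89.6 | 89.9 → 89.6 | 89.9 → 89.7 |
| 1.5 / 1.25 | 88.7 → 89.7 | 88.5 → 89.2 | 89.0 → 89.6 |
| 2 / 1.25 | 86.7 → 89.3 | 87.2 → 89.4 | 87.6 → 89.6 |

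At 1.25/1 the change is −0.1 to 0.0. At 3/1.25 the gain is 5.0 to 7.1 points.

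**5. Type I error (nominal 4.9%, 20,000 null trials).** Unstratified: 4.9–5.0% with inert strata, 4.2–4.5% at pain HR 2, 3.4–3.9% at HR 3. Stratified: 4.6–5.2% throughout. The HR 2 figures show the mechanism. A true level of 4.2% corresponds to z = 2.034, and (1.969/2.034)² = 0.94, so about 6% of the variance used is between-stratum variation. For 4.5% the share is about 4%.

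**6. Passing both active tests (equal HRs assumed; 15,000 three-arm trials).**

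| Pain HR / gender HR | Split A | Split B |
|---|---|---|
| 1 / 1 | 83.2 → 82.7 | 83.4 → 83.0 |
| 1.5 / 1.25 | 81.1 → 82.4 | 81.2 → 82.3 |
| 2 / 1.25 | 78.4 → 82.3 | 79.3 → 82.5 |

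**7. Weights matter.** Summing the within-stratum statistics without weights gives 85.0–85.7% power in split B and 82.9–83.1% in split C, below the planned unstratified test. U grows with the square of stratum size and V with the cube, so an unweighted sum over-weights the large strata.

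**8. Sensitivity to the model.** A second simulation used Weibull times (shape 1.0 or 1.5), 0% or about 15% never relieved, and four equal strata, with stratum effects as time ratios. The loss without stratification was 0.7–2.3 points at a pain ratio of 1.5 and 1.8–7.5 points at 2.

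**9. Onset endpoint.** 150 v 50, medians 17 and 120 minutes, 1,500 trials, split A. Mean earliest significant minute, unadjusted → adjusted: at alpha 0.05, 6.4 → 6.4 (inert) and 8.9 → 8.8 (2/1.25); at alpha 0.001, 13.0 → 12.9 and 19.3 → 18.6. Adjustment changes little here.

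**The case against.** The strongest reply is that nothing is wrong. SAP 4.4 and both code blocks agree with each other, the protocol names only the Wilcoxon test and logistic regression, and neither document promises a stratified analysis. That stands: this is about efficiency.

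Next, the size depends on a prognostic strength that the documents do not give. A gain of 2 points or more needs roughly a twofold pain effect. That also stands, and the HR 3 figures only mark the far end of the range.

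Third, the loss is measured from an effect size that gives 90% with inert strata. The modelling behind Protocol 14.1 may already include variation between subjects. The unstratified test would then have its 90%, and stratifying would raise it: in the Weibull simulation, to about 90–92% at a pain time ratio of 1.5 and 91–95% at 2. So the stated 90% is not shown to be wrong. The advantage of the stratified test remains either way.

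The joint-power figures assume equal effects against both comparators, although power is stated only for the tablet. A wrongly weighted stratified test can do worse than the planned one, so the statistic must be written out. Some planned TCPR outputs are blacked out, but SAP 4.4 makes a hidden adjusted analysis unlikely.

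**Conclusion.** The concern holds as a conditional efficiency point. The planned tests are valid and the TCPR comparison with placebo is safe. If gender or baseline pain predicts TCPR, leaving the strata out costs power on each active-comparator test: about 1 point or less at pain/gender HRs of 1.5/1.25, and 2.0 to 2.6 points at 2/1.25. At 2/1.25 the chance of passing both is lower by 3.2 to 3.9 points. With weak strata there is no gain, and with inert strata stratifying costs 0.2 to 0.3 point per test. These figures rest on the assumed prognostic strengths, severe share, exponential times and 10% never relieved; Weibull times with shape 1.5 give larger losses. It is worth considering because the likely gain exceeds the cost and the factors are already recorded.

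**What to change.** - **SAP 4.4:** replace the sentence with a statement that each pairwise TCPR comparison will use a Wilcoxon test stratified by gender and baseline categorical pain.
- **SAP 5.3.1:** write out the statistic in step 3 above, with weights 1/(stratum size + 1), and show the weights in the code. Do not sum the within-stratum statistics unweighted. In the primary analysis subjects without relief rank last and tied. For sensitivity analyses 1 and 2, which censor earlier, use the within-stratum Gehan-Wilcoxon U and V with the same weights.
- **Keep** the unstratified Wilcoxon test as a sensitivity analysis, and the unstratified Kaplan-Meier curves and medians for display.
- **SAP 5.3.2:** keep logistic regression and add gender and baseline pain to the model. This is mainly for consistency, and the odds ratio becomes conditional on the strata.
- If the strata are left out, give the reason in SAP 4.4.

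The cost is SAP text and code, changed before unblinding. The protocol needs no change: 14.7.1 does not say whether the Wilcoxon test is stratified, and 14.7.2 ("The dichotomized response will be analyzed using logistic regression analysis") is still met. No new data are needed. If the strata prove inert, the price is 0.2 to 0.3 point of power per comparison and 0.3 to 0.6 point for passing both active tests.
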